9.1.5. Partial Date Convention

Imputed dates will NOT be presented in the listings.

Table 10. Algorithm for Treatment Emergence of Adverse Events

Start Date	Stop Date	Action
Known	Known, Partial, or Missing	 If AE start date < study treatment first dose date, then not TEAE If AE start date ≥ study treatment first dose date, then TEAE
Partial, but known components show that it cannot be on or after date of first dose of study treatment	Known, Partial, or Missing	Not TEAE
Partial, could be on or after date of first dose of study treatment	Known	If AE stop date < study treatment first dose date, then not TEAE

Table 10. Algorithm for Treatment Emergence of Adverse Events

Start Date	Stop Date	Action
		If AE stop date ≥ study treatment first dose date, then TEAE
	Partial	Impute AE stop date as latest possible date (ie, last day of month if day unknown or 31st December if day and month are unknown), then: • If AE stop date < study treatment first dose date, then not TEAE • If AE stop date ≥ study treatment first dose date, then TEAE
	Missing	Assumed TEAE

Table 11. Algorithm for Prior and Concomitant medications

Start Date	Stop Date	Action
Known	Known	If medication stop date < study treatment first dose date, assign as prior
		If medication stop date ≥ study treatment first dose date, assign as concomitant
	Partial	 Impute stop date as latest possible date (ie, last day of month if day unknown or 31st December if day and month are unknown), then: If medication stop date < study treatment first dose date, assign as prior If medication stop date ≥ study treatment first dose date, assign as concomitant
	Missing	If medication stop date is missing could never be assumed a prior medication, assign as concomitant
Partial	Known	 Impute start date as earliest possible date (ie, first day of month if day unknown or 1st January if day and month are unknown), then: If medication stop date < study treatment first dose date, assign as prior If medication stop date ≥ study treatment first dose date, assign as concomitant

Table 11. Algorithm for Prior and Concomitant medications

Start Date	Stop Date	Action
	Partial	Impute start date as earliest possible date (ie, first day of month if day unknown or 1st January if day and month are unknown) and impute stop date as latest possible date (ie, last day of month if day unknown or 31st December if day and month are unknown), then: • If medication stop date < study treatment first dose date, assign as prior. • If medication stop date ≥ study treatment first dose date, assign as concomitant
	Missing	Impute start date as earliest possible date (ie, first day of month if day unknown or 1st January if day and month are unknown), then: If medication stop date is missing could never be
Missing	Known	assumed a prior medication, assign as concomitant If medication stop date < study treatment first dose date, assign as prior Else assign as concomitant
	Partial	 Impute stop date as latest possible date (ie, last day of month if day unknown or 31st December if day and month are unknown), then: If medication stop date < study treatment first dose date, assign as prior If medication stop date ≥ study treatment first dose date, assign as concomitant
	Missing	Assign as concomitant

Table 12. Algorithm for Starting Date of Hospitalization and Start/Stop Dates of Concomitant Medication

Start Date	Stop Date	Action
Partial	Partial	Impute start date as earliest possible date (ie, first day of month if day unknown or 1st January if day and month are unknown). Impute stop date to latest possible date (ie, last day of month if day unknown or 31st December if day and month are unknown).
		No partial stop date imputation for hospitalization

Table 12. Algorithm for Starting Date of Hospitalization and Start/Stop Dates of Concomitant Medication

Start Date	Stop Date	Action
Missing	Missing	Impute start date as informed consent date. Impute stop date as last visit date when the concomitant medication timepoint is not ongoing. No missing stop date imputation for hospitalization.

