9.9.9.1.5. Severity

The severity of each adverse event will be assessed at the onset by a nurse/or physician. When recording the outcome of the adverse event the maximum severity of the adverse event experienced will also be recorded. The severity of each adverse event will be graded according to the Common Terminology Criteria for Adverse Events (CTCAE), version 5.0:

Grade 1: Mild; asymptomatic or mild symptoms; clinical or diagnostic

observations only; intervention not indicated.

Grade 2: Moderate; minimal, local or noninvasive intervention indicated;

limiting age-appropriate instrumental activities of daily living (ADL).

Grade 3: Severe or medically significant but not immediately life-threatening;

hospitalization or prolongation of hospitalization indicated; disabling, limiting self-care ADL (eg, preparing meals, shopping for groceries or

clothes, using the telephone, managing money).

Grade 4: Life-threatening consequences, urgent intervention indicated.

Grade 5: Death related to adverse event.

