9.9.9.2.2. Recording Adverse Events

The adverse event reporting period for safety surveillance begins when the subject is initially included in the study (date of first signature of informed consent) and continues up to 30 days after the last administration of study treatment. If an adverse event is not resolved or stabilized by this time, the Sponsor in consultation with the Investigator will decide whether to continue to monitor the adverse event or closeout the event in the database if no further follow-up is necessary.

Investigators are not obligated to actively seek information on AEs or SAEs after the subject has concluded study participation. Any SAE suspected to be related to the study treatment must be reported whenever it occurs, irrespective of the time elapsed since the last administration of study treatment.

Investigators and study personnel will record all adverse events and SAEs whether received through an unsolicited report by a subject, elicited during subject questioning, discovered during physical examination, laboratory testing, and/or other means by recording them on the eCRF and/or SAE Form, as appropriate. The following information should be recorded on the adverse event eCRF:

- Description including onset and resolution dates
- Whether it met SAE criteria
- Severity
- Relationship to study treatment or other causality
- Outcome

For SAEs, events occurring secondary to the primary event should be captured and reported via the established safety reporting mechanism.

The following should be considered when recording SAEs:

- Death is an outcome of an event. The event that resulted in the death should be recorded and reported on the eCRF.
- For hospitalizations, surgical, or diagnostic procedures, the illness leading to the surgical or diagnostic procedure should be recorded as the SAE, not the procedure

itself. The procedure should be captured in the narrative as part of the action taken in response to the illness.

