3.2.2. Safety Endpoint(s)

3.2.2.1. Adverse Event

AEs will be coded using MedDRA (v27.0). The version used to code AEs will be displayed in the analyses. Treatment-emergent adverse events (TEAEs) are defined as AEs that started or worsened in severity on or after the first dose of study treatment.

Refer to Section 9.1.5 for handling of partial dates for AEs for the purpose of assigning treatment-emergent flags. In the case where it is not possible to define an AE as treatment-emergent or not, the AE will be classified as treatment-emergent.

Severity of TEAEs

Severity is classified as Grade 1: Mild, Grade 2: Moderate, Grade 3: Severe, Grade 4: Lifethreatening, Grade 5: Death related to AE, using the Common Terminology Criteria for Adverse Events, v5.0 (CTCAE v5.0).

Relationship of TEAEs to Study Treatment

Relationship is classified as "not related", "unlikely related", "probably related", or "related" by the Investigator.

TEAEs Leading to Discontinuation of Study Treatment

TEAEs leading to discontinuation of study treatment will be identified by action taken being recorded as "Drug withdrawal" on the Adverse Events electronic case report form (eCRF).

Serious and Non-Serious TEAEs

Serious adverse events (SAEs) are those events recorded as "Serious" on the Adverse Events eCRF.

TEAEs Leading to Death

TEAEs leading to Death are those events which are recorded with an outcome as "Fatal" on the Adverse Events eCRF.

TEAEs of Special Interest

Categories of Targeted Medical Events (TMEs) and a list of preferred terms associated with these TME categories were developed based on the mechanism of action of etrasimod, prior experience with other agents acting via a similar mechanism, and disease-specific clinical judgment. The proposed candidate terms will be reviewed along with other supportive data (eg, vital signs, lab) to identify which events reflect AESI.

Categories and subcategories of TEAEs of special interest are the following:

- Cardiovascular Events
 - Bradycardia
 - AV conduction delay
 - Hypertension
- Macular Edema
- Pulmonary Disorders
 - Airflow obstruction (forced expiratory volume in 1 second [FEV1], forced vital

- capacity [FVC])
- Decrease gas exchange (diffusing capacity of the lungs for carbon monoxide
- [DLCO]
- Infections
 - Severe infections
 - Opportunistic infections (Narrow)
 - Herpes simplex and herpes zoster
- Liver Injury
 - Liver transaminases elevation
 - Bilirubin elevation

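### Table 10 of the SAP leaves out the worsening half of the TEAE definition, so a screening-onset AE that worsens on treatment and stays on one record is flagged as not treatment-emergent

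*SAP*

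**What the plan says.** SAP 3.2.2.1 gives the definition. TEAEs "are defined as AEs that started or worsened in severity on or after the first dose of study treatment". There are two separate routes in: a new start, or a rise in severity. The section then points elsewhere for the flag: "Refer to Section 9.1.5 for handling of partial dates for AEs for the purpose of assigning treatment-emergent flags". It adds a default: an event that cannot be classified either way counts as treatment-emergent.

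Table 10 in SAP 9.1.5 is titled as the algorithm for treatment emergence. Its rows are as follows.

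- Known start date, any stop date: "If AE start date < study treatment first dose date, then not TEAE"; otherwise TEAE.
- "Partial, but known components show that it cannot be on or after date of first dose of study treatment": not TEAE, any stop date.
- "Partial, could be on or after date of first dose of study treatment": decided by the stop date. It is a TEAE if the stop date, imputed as late as possible when partial, is not before first dose, or if it is missing.

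No row uses severity or a date of worsening.

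On collection, Protocol 9.9.9.2.2 opens the AE reporting period at informed consent. Protocol 9.9.9.1.5 has severity assessed at onset and then adds: "When recording the outcome of the adverse event the maximum severity of the adverse event experienced will also be recorded". The eCRF items listed in Protocol 9.9.9.2.2 include onset and resolution dates, seriousness, severity, relationship and outcome. A date of worsening is not among them.

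**The concern.** Screening lasts 28 days and can be extended (Protocol 9.3), and participants have active ulcerative colitis, so some AEs will begin between consent and first dose. If one of these becomes more severe on treatment, the definition says to count it and the algorithm says not to.

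The flag feeds all of SAP 6.3.1: the summaries by system organ class and preferred term, exposure-adjusted rates, maximum severity, relationship, seriousness, discontinuation and interruption, the special-interest Cox model, and the comparative analyses of grade 3 or higher, serious and discontinuation TEAEs. An event that began in screening, worsened on treatment and led to withdrawal of study drug would be missing from the table of TEAEs leading to discontinuation. Worsening of existing events is part of what a placebo-controlled safety comparison should show, and the plan's own definition says it will be shown.

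**Working it through.** The plan states no figure to reproduce. The check applies the 3.2.2.1 definition and the Table 10 rules to the same cases and compares the answers. In every case below the event is still ongoing at first dose, with a stop date after first dose or missing.

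| Start date | Severity rises after first dose | SAP 3.2.2.1 | Table 10 |
|---|---|---|---|
| Known, before first dose | No | Not TEAE | Not TEAE |
| Known, before first dose | Yes | **TEAE** | **Not TEAE** |
| Partial, certainly before first dose | No | Not TEAE | Not TEAE |
| Partial, certainly before first dose | Yes | **TEAE** | **Not TEAE** |
| Partial, ambiguous, truly before first dose | No | Not TEAE | TEAE |
| Partial, ambiguous, truly before first dose | Yes | TEAE | TEAE |
| After first dose (known or ambiguous partial) | Either | TEAE | TEAE |

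Reading the table:

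1. Where the start is known, or shown by its partial date, to be before first dose, the two rules disagree whenever severity rises after first dose. This holds whether the stop date is known or missing.
2. With an ambiguous partial start, Table 10 returns TEAE with or without worsening. The worsened event is kept because of its dates, not because it worsened. The mismatch in the fifth row is a cautious date convention and is not part of this point.
3. The 3.2.2.1 default does not rescue the cases in step 1. It applies when classification is impossible, and here Table 10 gives a definite answer.
4. The section heading does not rescue them either. Section 9.1.5 is headed as a convention for partial dates, but the first row of Table 10 covers fully known start dates.

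Size: the documents give no count of screening-onset AEs and no rate of worsening. Purely as an illustration, assume that 5% to 10% of the planned 225 or so participants have an AE from screening still ongoing at first dose, and that 10% to 20% of those events worsen:

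- low: 225 × 0.05 × 0.10 = 1.1 participants
- high: 225 × 0.10 × 0.20 = 4.5 participants

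Both rates are assumptions with no source in the documents. The result shows only that a small number is plausible.

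**The case against.** The strongest reply is that the worsening may be counted by another route. Protocol 9.9.9.1.1 lists a preexisting condition that gets worse among the things that can be an AE, and footnote d of the Schedule of Assessments has medical history updated for new conditions before Day 1 dosing. A problem arising in screening could therefore sit in medical history, and its later worsening could be entered as a fresh AE with an on-treatment onset. Table 10 would flag that as a TEAE. Protocol 9.9.9.1.5 does not say whether a change in severity extends the old record or opens a new one, and the eCRF completion rules are not among the documents.

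This stands as a limit. A reader might infer that on-treatment worsening is never counted, or that Table 10 discards every event that began before first dose. The documents support neither reading: worsening entered as a new record is counted, and ambiguous partial starts can be flagged TEAE. The limit does not remove the conflict. Neither document tells sites to open a new record for an AE already logged in screening, and recording one maximum severity per event points towards a single record.

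A second reply is that Table 10 covers only the onset half of the definition and leaves the worsening half in force. No programming specification is available to exclude that. But the table's title, its row for known dates and the pointer from 3.2.2.1 all invite a programmer to treat it as the whole rule.

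Third, nothing disappears from the report. SAP 6.3.1.1 lists every AE whatever its flag, and SAP 6.5.2 summarises reasons for stopping treatment. That is true, but a listing does not replace the between-group summaries and comparisons.

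**Conclusion.** The inconsistency is real and lies in the rule behind every TEAE table. It affects AEs whose start is known, or shown by a partial date, to be before first dose, that become more severe from first dose onward, and whose worsening stays on the original record. Those events meet the definition in SAP 3.2.2.1 and are excluded by Table 10.

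The number affected cannot be derived from the documents and is probably small. The conclusion depends on how sites record worsening, which the documents leave open.

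A reader might go further and infer that the safety results will favour etrasimod. The documents do not support that. The same rule applies to both arms, and the omission understates etrasimod's risk only if etrasimod aggravates such events more than placebo does, which nothing in the documents establishes.

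**What to change.** Before unblinding:

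1. Add a row to Table 10, applying to known starts before first dose and to partial starts that must precede it: if severity increased from first dose onward, the event is a TEAE.
2. Where severity increased, the timing of the increase cannot be determined and the event was ongoing at first dose, apply the default already in SAP 3.2.2.1 and classify it as treatment-emergent.
3. State whether worsening is captured as a new AE record or on the original one, and what date, if any, is recorded for it.
4. Say which date serves as onset for these events. SAP 6.3.1.1 measures exposure from first dose to onset, and the Cox model in SAP 6.3.1.4 uses event start dates, so a pre-dose date would not work in either.

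Keep the trigger to severity. Making a change to serious a further trigger would go beyond the SAP's own definition. If the sponsor does not intend to count worsening, the alternative is to delete that half of the definition in 3.2.2.1 and narrow it openly.

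The cost is one table row, a short statement on recording and a small programming change. The downside is a few more TEAEs. If only onset and maximum severity are held, many of these events will fall to the default in step 2, and some will have worsened during screening. That errs in the direction SAP 3.2.2.1 already chooses for unclear cases.

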9.1.6. Protocol Deviation Categories

Protocol deviation categories include but are not limited to the following:

- Informed consent and Process
- Inclusion criteria
- Exclusion Criteria
- Concomitant Medication
- PK/PD
- Laboratory Assessment
- Study Procedures
- Patient Reported Outcome
- Safety
- Efficacy
- IP Administration
- Visit Schedule
- IP Conditions
- Participant IP Compliance
- Participant Discontinuation
- Randomization
- Administrative

Other

9.1.7. Hourly Timepoint Determination in Cardiac Analysis

Based on dosing date/time, the cardiac central laboratory divided the collection period into 60-minute intervals (eg, from dosing time to dosing time + 60 minutes, from dosing time + 60 minutes to dosing time + 120 minutes, etc.). In some cases, recording from a partial hourly interval was used to derive hourly data if the Holter recording end time didn't coincide with a multiple of 60 minutes from dosing. For Holter recording data before dosing, per study design, each participant is expected to have one pre-dose Holter record with a duration of about 15 minutes. However, there may exist multiple pre-dose Holter records derived by the cardiac central laboratory for the same participant, based on every 60-minute increment backwards from dosing time until the overall Holter start time is reached. Similarly, pre-dose (eg, hour 0) data may be based on recording from a partial hourly interval, depending on Holter recording start/stop time relative to dosing.

The hourly timepoint will be programmatically calculated as the Holter hourly data stop time minus dosing time, converted to hours and rounded to the nearest whole number. If there are more than 1 hourly timepoint from this derivation, the latter one will be assigned to the next whole hourly timepoint. This applies to both pre-dose and post-dose timepoints.

9.2. Endpoint Derivations

9.2.1. WPAI-UC Scoring Rules

The Work Productivity and Activity Impairment Questionnaire — Ulcerative Colitis (WPAI-UC) questionnaire was developed to measure the effect of general health and symptom severity on work productivity and regular activities. The questionnaire includes the following questions.

Questions:

- 1 = Are you currently employed?
- 2 = During the past seven days, how many hours did you miss from work due to your problems associated

with UC?

- 3 = During the past seven days, how many hours did you miss from work because of any other reasons?
- 4 = During the past seven days, how many hours did you actually work?
- 5 = During the past seven days, how much did your UC affect your productivity while you were working?
- 6 = During the past seven days, how much did your UC affect your ability to do your regular daily activities, other than work at a job?

Derivation:

- 1) Calculate work time missed score as: Q2/(Q2 + Q4)
- 2) Calculate impairment while working score as: Q5/10
- 3) Calculate overall work impairment score as: $Q2/(Q2 + Q4) + [(1 Q2/(Q2 + Q4)) \times (Q5/10)]$

4) Calculate activity impairment score as: Q6/10

Multiply each score by 100 in order to express as percentages.

9.2.2. IBDQ Scoring Rules

The Inflammatory Bowel Disease Questionnaire (IBDQ) is a 32-item self-administered questionnaire which has 4 dimensions: Bowel symptoms (10 items), systemic symptoms (5 items), emotional health (12 items), and social function (5 items). Responses are graded on a 7-point Likert scale where 7 denotes "not a problem at all" and 1 denotes "a very severe problem". Scores range from 32 to 224, a higher score indicates better quality of life.

The 4 dimensions are defined as:

- Bowel symptoms: Questions 1, 5, 9, 13, 17, 20, 22, 24, 26, 29
- Systemic symptoms: Questions 2, 6, 10, 14, 18
- Emotional health: Questions 3, 7, 11, 15, 19, 21, 23, 25, 27, 30, 31, 32
- Social function: Questions 4, 8, 12, 16, 28

A IBDQ total score can also be calculated as the sum of all 32 items.

9.2.3. SF-36 Scoring Rules

The Medical Outcomes Study 36 Item Short Form Health Survey (SF-36) is a 36-item self-administered questionnaire which has 8 scales: Physical functioning (10 items), role limitations due to physical health (4 items), role limitations due to emotional problems (3 items), vitality (4 items), mental health (5 items), social functioning (2 items), bodily pain (2 items), and general health (5 items). Each item response is scored from 0 to 100 and items in the same scale are averaged together to create 8 subscores. Scores range from 0 to 100. A higher score indicates a more favorable health state.

The 8 dimensions are defined as:

- Physical functioning: Questions 3 to 12
- Role limitations due to physical health: Questions 13 to 16
- Role limitations due to emotional problems: Questions 17 to 19
- Vitality: Questions 23, 27, 29, 31
- Mental health: Questions 24 to 26, 28, 30
- Social functioning: Questions 20, 32

• Bodily Pain: Questions, 21, 22

• General health: Questions 1, 33 to 36

9.3. Classification of Rescue Therapy

This appendix outlines the algorithm for the Pfizer clinical team/medical reviewers to classify rescue therapies for ulcerative colitis (UC) in a blinded manner. This will help establish intercurrent events for the efficacy estimands. All rescue therapies identified by the medical reviewers per the algorithm below will be imported in programming. This process will be repeated until database lock and the list of all rescue therapies identified will be finalized before study unblinding.

Only medications and medical procedures reported on the electronic case report forms (eCRFs) can be assessed whether they are rescue therapy for UC. If the exposure happens in the follow-up period (beginning on or after the date of last study treatment administration), then it would not be considered as a rescue therapy. Impact of rescue therapy use in the analysis is timing-dependent, eg, if a participant starts a rescue therapy between their Week 12 and Week 52 endpoint assessments, then it may have potential impact on Week 52 endpoint analysis but will have no impact on Week 12 endpoints. The rules outlined below apply to both new use and increase in dose from Baseline.

Biologics with immunomodulatory properties

- Rule:
 - Any exposure after first dose
- List of medications:
 - AntiTNFα antibodies:
 - ADALIMUMAB
 - CERTOLIZUMAB
 - CERTOLIZUMAB PEGOL
 - GOLIMUMAB
 - INFLIXIMAB
 - Other Biologics:
 - USTEKINUMAB
 - VEDOLIZUMAB
 - MIRIKIZUMAB

Nonbiologics with immunomodulatory properties

- Immunosuppressants
 - Rules to consider for Week 12 efficacy endpoints:
 - After first dose and up to and including Week 8: any increase from baseline for more than 5 days
 - After Week 8: Any dose above baseline
 - Rules to consider for Week 52 efficacy endpoints:
 - After Week 12 and up to and including Week 40: any increase from baseline for more than 5 days
 - After Week 40: Any dose above baseline
 - List of medications:
 - Thiopurines
 - MERCAPTOPURINE
 - o AZATHIOPRINE
 - TIOGUANINE
 - METHOTREXATE
 - METHOTREXATE SODIUM
- 5-ASA COMPOUNDS
 - Rules to consider for Week 12 efficacy endpoints:
 - After first dose and up to and including Week 8: any increase from baseline for more than 5 days
 - After Week 8: Any dose above baseline
 - Rules to consider for Week 52 efficacy endpoints:
 - After Week 12 and up to and including Week 40: any increase from baseline for more than 5 days
 - After Week 40: Any dose above baseline

- List of medications:
 - MESALAZINE
 - MESALAMINE
 - BALSALAZIDE
 - BALSALAZIDE DISODIUM DIHYDRATE
 - BALSALAZIDE SODIUM
 - OLSALAZINE SODIUM
 - SULFASALAZINE
 - BECLOMETASONE W/MESALAZINE
- Routes:
 - ORAL
 - RECTAL

Other small molecule immunomodulatory active agents

- Rules to consider for Week 12 efficacy endpoints:
 - After first dose and up to and including Week 8: any increase from baseline (including new use) for more than 5 days
 - After Week 8: Any dose above baseline
- Rules to consider for Week 52 efficacy endpoints:
 - After Week 12 and up to and including Week 40: any increase from baseline (including new use) for more than 5 days
 - After Week 40: Any dose above baseline
- List of medications:
 - CICLOSPORIN
 - TACROLIMUS
 - TOFACITINIB
 - TOFACITINIB CITRATE

- UPADACITINIB
- Systemic glucocorticoids
 - Systemic glucocorticoids given via oral or rectal routes of administration
 - Rules to consider for Week 12 efficacy endpoints:
 - After first dose and up to and including Week 8: any increase from baseline for more than 7 days
 - After Week 8: Any dose above baseline
 - Rules to consider for Week 52 efficacy endpoints:
 - After Week 12 and up to and including Week 40: any increase from baseline for more than 7 days
 - o After Week 40: Any dose above baseline
 - List of medications:
 - BETAMETHASONE
 - BETAMETHASONE DIPROPIONATE
 - BETAMETHASONE SODIUM PHOSPHATE
 - DEXAMETHASONE
 - DEXAMETHASONE SODIUM PHOSPHATE
 - DEXAMETHASONE VALERATE
 - METHYLPREDNISOLONE
 - METHYLPREDNISOLONE SODIUM SUCCINATE
 - o PREDNISOLONE
 - PREDNISOLONE SODIUM PHOSPHATE
 - PREDNISOLONE METASULFOBENZOATE SODIUM
 - o PREDNISONE
 - TRIAMCINOLONE
 - HYDROCORTISONE

- HYDROCORTISONE ACETATE
- HYDROCORTISONE BUTYRATE
- HYDROCORTISONE SODIUM SUCCINATE
- Routes:
 - o ORAL
 - o RECTAL
- Systemic given via parenteral routes of administration
 - Rule for Week 12 endpoint:
 - Any exposure after first dose up to Week 12
 - Rules for Week 52 endpoint:
 - After Week 12 and up to and including Week 40: more than one dose
 - Any exposure after Week 40
 - List of medications:
 - BETAMETHASONE
 - BETAMETHASONE DIPROPIONATE
 - BETAMETHASONE SODIUM PHOSPHATE
 - DEXAMETHASONE
 - DEXAMETHASONE SODIUM PHOSPHATE
 - DEXAMETHASONE VALERATE
 - METHYLPREDNISOLONE
 - METHYLPREDNISOLONE SODIUM SUCCINATE
 - PREDNISOLONE
 - PREDNISOLONE SODIUM PHOSPHATE
 - PREDNISOLONE METASULFOBENZOATE SODIUM
 - PREDNISONE

- TRIAMCINOLONE
- HYDROCORTISONE
- HYDROCORTISONE ACETATE
- HYDROCORTISONE BUTYRATE
- HYDROCORTISONE SODIUM SUCCINATE
- Routes:
 - INTRAVENOUS
 - INTRAMUSCULAR
- Topical Glucocorticoids
 - Rules for Week 12 endpoints:
 - After first dose and up to and including Week 8: any exposure above baseline (or new use) for more than 5 days
 - After Week 8: Any dose above baseline
 - Rules for Week 52 endpoints:
 - After Week 12 and up to and including Week 40: any increase from baseline for more than 5 days
 - After Week 40 any increase above baseline
 - List of medications:
 - BUDESONIDE
 - Routes:
 - ORAL
 - RECTAL
- Beclomethasone
 - Rules for Week 12 endpoints:
 - After first dose and up to and including Week 8: Any increase above baseline for more than 5 days

- After Week 8: Any dose above baseline
- Rules for Week 52 endpoints:
 - After Week 12 and up to and including Week 40: Any increase from baseline for more than 5 days
 - After Week 40 any increase above baseline
- List of medications:
 - BECLOMETASONE

Medical procedures

- Leukocyte apheresis, other apheresis, and plasma exchange
 - Rule:
 - Any exposure after first dose
 - List of medical procedures
 - APHERESIS
 - LEUKAPHERESIS
 - COLECTOMY (partial or total)
 - SIGMOIDECTOMY
 - COLOSTOMY
 - ILEOSTOMY

